Protocol for the HYPER-study

Contents

1. Title	1
2. Aim	1
3. Methods	4
4. Statistical considerations	5
5. The study participants	5
6. Risks, side effects, and disadvantages in the short and long term	6
7. Collection of new biological material or retrieval of biological material from an existing biobank	
8. Information from patients' records	6
9. Handling of personal data in the project	8
10. Transmission of personal data/biological material abroad	8
11. Economy	8
12. Any compensation and/or other benefits for the trial participants.	9
13. Recruitment of trial participants and informed consent	9
14. Publication of results	10
15. Ethical considerations	10
16. Information about insurance	10

1. Title

English: Hyperexcitability as a Predictor of Epilepsy Risk in Glioblastoma (HYPER-study) Danish: Hyperexcitabilitet til forudsigelse af epilepsi hos patienter med glioblastom

2. Aim

a. Problem statement, hypothesis, endpoints, and rationale:

Recent advances in research on brain tumors, called gliomas, have improved our understanding of its molecular biology but have not significantly enhanced survival or quality of life. Evidence suggests that neuron-glioma interactions drive tumor growth, disrupting brain networks and causing epileptic seizures, leading to worse outcomes. However, not all tumors follow this pathway, and we cannot yet predict which patients will develop seizures. By integrating clinical data, genomics, and real-time brain activity measurements, our ambition is to identify patients at high risk of developing seizures. By highlighting three different aspects of epilepsy (diagnosis, seizures, and medication), we can obtain valuable data to support or disprove our hypothesis about epilepsy's negative impact on brain cancer. The results can be used to design clinical trials aiming at improved personalized treatment.

Our hypothesis is that epilepsy-related high-grade gliomas represent a clinical and molecular subgroup of gliomas with increased synaptic activity that drives tumor growth thereby causing a poorer prognosis for the patients.

The aim of the HYPER study is to investigate how hyperexcitability is related to development of epilepsy, seizure control, and survival in patients with glioblastoma.

Hyperexcitability will be measured using subcutaneous EEG.

The endpoints for this study are development of epilepsy, seizure control, overall survival, and progression-free survival.

The HYPER study is the first to investigate hyperexcitability as a potential early driver of tumor progression in glioblastoma patients. If hyperexcitability is shown to contribute to tumor growth, future clinical trials should focus on targeting hyperexcitability to achieve tumor control. The overarching goal is to enhance overall survival.

b. Short review of literature:

Glioblastoma is the most common and aggressive primary brain tumor in adults¹. Treatment consists of maximal safe resection, radiotherapy, and chemotherapy. Despite this the median overall survival for glioblastoma is only 15 months².

Epilepsy is one of the most common symptoms in gliomas³⁻⁵. Glioma-related epilepsy (GRE) negatively impacts quality of life⁶. GRE treatment with anti-seizure medication (ASM) is given following the first epileptic seizure to achieve durable seizure control and improved quality of life.

In patients with epilepsy, the neurons are both firing too much and too synchronized. Hyperexcitability is a term used in this area of research to describe the excessive firing of neurons. Preclinical studies show that excessive firing between glioma cells and neurons drive glioma growth and invasiveness and that treatment with ASM inhibits tumor growth^{7,8}. A recent large epidemiological study found that patients with epileptic seizure after glioma diagnosis had a significantly poor prognosis⁹. Taken together these studies suggest hyperexcitability and GRE drive glioma growth and negatively impact survival in HGG patients.

In clinical practice, hyperexcitability can be measured with electrodes placed on the scalp called electroencephalogram (EEG). An EEG from a patient with epilepsy can reveal specific hyperexcitable electric patterns described as interictal epileptic discharges (IEDs)¹⁰. In contrast to the standard 30-minute scalpEEG, a novel device has been developed by a Danish company (UNEEG) to continuously monitor electrical activity using electrodes under the skin (subcutaneous EEG (scEEG))¹¹. The device is CE marked and we will use it as an instrument to continuous, long-term, EEG monitoring to improve the detection of IEDs and seizure activity compared to routine 30-minute EEG. Routine EEG often fails to capture transient abnormalities due to its short duration, leading to missed diagnoses. In contrast, scEEG enables prolonged recording, increasing sensitivity to rare events and providing a more comprehensive assessment of seizure patterns. Additionally, scEEG improves diagnostic accuracy in

patients with infrequent seizures, allowing for treatment optimization. Its minimally invasive nature makes it suitable for outpatient settings, enhancing patient comfort and compliance while reducing hospitalization needs. Thus, this device enables continuous investigation of hyperexcitability as part of epilepsy and tumor development – this causal relationship has only been studied in laboratory experiments. Knowledge from patients could confirm and shed light on this disease mechanism, potentially leading to better treatment. A video about the scEEC can be found via

treatment. A video about the scEEG can be found via the QR code, or via this link: https://vimeo.com/1006556953?share=copy.

References:

- 1 Ostrom, Q. T. *et al.* CBTRUS Statistical Report: Primary Brain and Other Central Nervous System Tumors Diagnosed in the United States in 2016-2020. *Neuro Oncol* **25**, iv1-iv99 (2023). https://doi.org/10.1093/neuonc/noad149
- 2 Stupp, R. *et al.* Radiotherapy plus concomitant and adjuvant temozolomide for glioblastoma. *N Engl J Med* **352**, 987-996 (2005). https://doi.org/10.1056/NEJMoa043330
- 3 Mahaley, M. S., Jr. & Dudka, L. The role of anticonvulsant medications in the management of patients with anaplastic gliomas. *Surg Neurol* **16**, 399-401 (1981). https://doi.org/10.1016/0090-3019(81)90227-5

The HYPER study is an observational cohort study. There will be no control group, randomization, or use of placebo.

Hyperexcitability

To measure neuronal hyperexcitability in real-life settings, patients will undergo a scEEG.

Neuronal hyperexcitability will be defined as the presence of IEDs on the scEEG.

The scEEG will be inserted in the period from end of radiotherapy till first MRI evaluation after two cycles of adjuvant chemotherapy (Figure "Study flow"). Recordings from the device will start after implantation.

A specialized AI analytic software for managing long term EEG data will be used to highlight suspected IEDs that can be reviewed by a clinical neurophysiologist to determine if these episodes show epileptiform discharges^{11,12}.

Epilepsy

All patients who develop epilepsy will be treated at Rigshospitalet by [name], clinical professor in neurology with a special focus on epilepsy. Patients will be treated with standard treatment for epilepsy according to national guidelines¹³.

b. The practical implementation, examinations, and scope

Patients will be informed and included via the Department of Cancer Treatment at Rigshospitalet. Detailed inclusion process is described in section 13. The doctors and nurses at the department are experienced in including patients for clinical trials.

A neurosurgeon ([name], neurosurgeon at the Department of Neurosurgery, Rigshospitalet) will place a scEEG device under the skin behind the patient's ear closest to the tumor. The device is inserted under local anesthesia in 20 minutes. The electrodes can be inserted with different directions and will be positioned closest to the tumor.

The scEEG will be explanted after fifteen months with the possibility of extension in case the scEEG device is approved for longer implantation. The scEEG does not need to be removed before cremation.

Patients will have an extra visit at Rigshospitalet when the scEEG is implanted and one when it is explanted. Patients who develop epilepsy might have extra visits at Rigshospitalet in relation to treatment with ASM. Otherwise, there will not be extra visits needed for participation in the study.

c. Deviations from standard treatment

There will be no deviations from standard treatment both regarding tumor and epilepsy treatment.

4. Statistical considerations

a. Power analysis

This study is explorative, and no studies have used scEEG to identify IEDs in brain tumor patients before. Therefore, making assumptions for power analysis is challenging since no data is available from similar study designs.

Our endpoints are development of epilepsy, seizure control, progression free survival and overall survival.

Based on current data from our clinical database the number of patients needed for this study is estimated to be fourteen patients. The level of significance is 2.5% one sided and the power 80%. The sample size is determined under the following assumptions: the proportion of patients having epilepsy is 50%, and the sensitivity for epilepsy with hyperexcitability is 85% or better. The null hypothesis is diagnostic accuracy = 0.5 against the alternative that diagnostic accuracy > 0.5.

5. The study participants

- a. Inclusion criteria:
 - Patients who have consented to the Neurogenom protocol¹⁴
 - Patients 18 years of age or older
 - Patients diagnosed with glioblastoma, IDH wild type grade 4
 - Patients treated with standard therapy at Rigshospitalet, Department of Cancer Treatment
 - Patient with a tumor located in a region where scEEG is expected to provide adequate signal quality
 - Performance status 0-1
 - Patients willing and able to use the scEEG, UNEEG EpiSight solution, day and night for the duration of the study
 - Patients willing and able to provide written informed consent
 - Patients able to understand the consequences of participation
 - Patients able to complete all study-required procedures, assessments and follow-up
- b. Exclusion criteria:
 - Patients who have a diagnosis of epilepsy
 - Patients treated with ASM
 - Pregnancy
 - High risk of surgical complications as assessed by the neurosurgeon
 - Involved in therapies with medical devices that deliver electrical energy into the area around the implant, such as cochlear implant(s), implantable brain stimulation and external/transcranial brain stimulation
 - Contraindications to the local anesthetic used during implantation and explantation

6. Risks, side effects, and disadvantages in the short and long term.

a. Safety measures that minimize pain, discomfort, fear, and other risks

Local anesthesia is used for implantation to minimize pain and discomfort under the procedure. As with any type of surgery there is risk of bleeding, infection, and nerve damage. After implantation there is a risk of displacement of the scEEG and irritation/inflammation around the implant. Patients will receive thorough information on signs of inflammation and instructions on how to wash the area behind the ear to minimize the risk of irritation and infection. Also, the patient will be provided with contact information of the Department of Neurosurgery who they can contact directly at any time of the day if they have concerns about the implant. The patients will be given contact information of the principal investigator in case of other study related concerns.

To date about two hundred people has had the scEEG implanted. No systematic collection of side effects is available concerning the scEEG. The estimated infection rate is 2-4 %. In the UK, one incidence of skin penetration due to surgeon error during the implantation has been reported.

b. Risk of radioactive radiation

There is no risk of radioactive radiation

7. Collection of new biological material or retrieval of biological material from an existing biobank

For the HYPER study no new biological material will be collected.

8. Information from patients' records

a. Disclosure without consent

Describe:

- i. Whether it is necessary to disclose information to identify/recruit study participants: It is not necessary to share information with others about the patients to identify them. They will all be treated at the Department of Cancer Treatment at Rigshospitalet.
- ii. Whether an exemption from obtaining consent is being sought or whether data from the patient record will be included without consent:

There will be no exemptions from obtaining consent and no data will be included without consent.

- iii. Whether a retrospective control group will be included: No retrospective control group will be included
- iv. For all categories it must be described:a. What specific information that need to be disclosed

Not applicable in this context.

b. The purpose

Not applicable in this context.

- c. How many patient records it concerns Not applicable in this context.
- d. What time period the information from the patient records is from Not applicable in this context.
- v. It must be stated that the information to be used in the project is disclosed to the researcher before consent has been given by the study participants

Only the doctors at the Department of Cancer Treatment will have access to the patients records before consent has been given. Information before consent is not shared with others.

- b. Use of patient record information with consent (after inclusion) Describe:
 - i. Which specific information will be collected for the trial Listed below
 - ii. The purpose (how they contribute to clarifying the projects hypotheses)

Category	Purpose	
Name	For identification	
CPR number		
Diagnosis		
Pathology report		
Performance status	To show characteristics of the cohort	
MRI		
Medication		
New symptoms (e.g., paralysis)	For correlation with hyperexcitability	
Seizures		
ASM dosage and start/end dates		
Date of progression		
Date of death		
Side effect to ASM	For ASM treatment adjustments	
Side effect of the implant	To monitor if explantation is needed	

iii. It must be stated that the consent grants the trial responsible, sponsor, and sponsor's representatives, as well as any regulatory authority, direct access to obtain information from the patient's medical records, including electronic records. This access is intended to review information about the participant's health conditions necessary for conducting the research project and for control purposes, including self-monitoring, guality control, and monitoring, which they are obligated to perform.

This information will be given to the patients before inclusion: Consent grants the trial responsible, sponsor, and sponsor's representatives, as well as any regulatory authority, *direct* access to obtain information from the patient's medical records, including electronic records. This access is intended to review information about the participant's health conditions necessary for conducting

the research project and for control purposes, including self-monitoring, quality control, and monitoring, which they are obligated to perform

9. Handling of personal data in the project

a. You must state that "databeskyttelsesforordningen" and "databeskyttelsesloven" are being complied with

"Databeskyttelsesforordningen" and "databeskyttelsesloven" are being complied with, and patients will get information about this with the written consent.

The project will be registered in the Capital Regions research database Privacy.

10. Transmission of personal data/biological material abroad

Data will not be sent abroad.

11. Economy

- a. Describe who has initiated the trial The principal investigator ([name]) and her supervisors ([name] and [name]) have initiated this study.
- b. Name of sponsors, including the amount for each sponsor.

This project is sponsored by Krogh Invest ApS. Total amount: 3.300.000 DKK Replies on applications for other sponsors to cover cost of the scEEG are awaiting. The committee and the study participants will be informed of any funding received as it becomes available.

c. How the support is incorporated into the trial

Krogh Invest ApS is sponsoring salary (full time for [name], part time for [name], part time for statistician) and operating cost.

Kategori	Beskrivelse	Beløb i DKK
Videnskabelig arbejdskraft	Løn, PhD-studerende, 36 måneder	2.100.000
Videnskabelig arbejdskraft	Løn, Postdoc, 12 måneder	700.000
Videnskabelig arbejdskraft	Løn, statistiker, 2 måneder	100.000
Udstyr	scEEG'er	1.200.000
Drift	Dataindsamling, publikationsudgifter	300.000
	mm	
	Total	4.500.000

Budget

d. Whether the support is paid directly to the researcher, their department/institute, a research fund, or another entity.

The support is paid to a research account managed by the Department of Cancer Treatment.

e. Whether the researcher has financial ties to the sponsor or other stakeholders in the trial None of the researchers have financial ties to the sponsor

12. Any compensation and/or other benefits for the trial participants.

The participating patients do not receive any compensation.

13. Recruitment of trial participants and informed consent

Describe the recruitment process as well as the procedure for providing oral information and obtaining consent:

a. How the trial participants are found and identified

Patients will be identified through visits to the Department of Cancer Treatment at Rigshospitalet.

b. How the initial contact with the trial participant takes place

Patients have regular visits at the hospital during the six weeks of radio-/chemotherapy. During these visits, patients will be made aware about the study by nurses or doctors at the Department of Cancer Treatment. If the patient is interested in participation, they will be referred to the principal investigator or to one of the doctors who have received training in patient enrollment and have consequently been delegated the responsibility for including patients in the study. The trial participant and the principal investigator or delegated doctor will then meet at the Department of Cancer Treatment, and the trial participant will be informed about the study.

- c. Process of obtaining informed consent
 - i. Where, when, and who provides the oral and written information

The patient will receive written and oral information about the study either by the principal investigator or the delegated doctor. This visit is voluntary and will take place at the Department of Cancer Treatment.

All relevant doctors at the department will be trained in patient enrollment and consequently be delegated the responsibility for including patients in the study. The delegation log will be attached to this application.

The written and oral information will be given in the period from start of radio-/chemotherapy till first MRI evaluation after radio-/chemotherapy. See attached figure "Study flow".

- How it is ensured that the discussion takes place undisturbed Consultations with patients and their relatives will be in a private and undisturbed room during their visit to the Department of Cancer Treatment.
- iii. How the right to a companion is ensured The nurses and doctors at the department will tell the patients about the right to an accompanying person before the information meeting with the principal investigator or delegated doctor.

iv. The reflection period between receiving oral and written information and providing informed consent

The patients will have a right for >24 hours of reflection time.

v. When consent is sought

Consent is obtained once the patient has had sufficient time to reflect. Consent can be given to either the principal investigator or delegated doctor. Consent can be given eighter at the next scheduled visit to the department or at an extra visit.

14. Publication of results

Both positive, negative, and inconclusive results will be published in international peerreviewed scientific journals. If publication is not achieved, the results will be disseminated through alternative methods, such as presentation at conferences.

15. Ethical considerations

The study will be conducted in accordance with ethical guidelines for medical research involving human subjects, as outlined in the Declaration of Helsinki.

Participation in the study is entirely voluntary, and patients can withdraw at any time without consequences for their standard treatment. If a patient decides to withdraw, their data will be removed from the study unless they consent to continued use.

Describe:

- a. Why the risks are not, in themselves or in relation to the benefits of the trial, irresponsible As described in section 6 only one side effect directly associated with the procedure has been reported out of two hundred procedures. Experiences from previous implantations have helped minimize the risk of errors in upcoming procedures.
- b. Why the therapeutic benefit for the trial participants or future patients justifies the study Based on the very modest risks and inconveniences, as well as the therapeutic benefits for future patients through more effective and targeted treatment, it is considered scientifically and ethically justifiable and warranted to conduct this project.

16. Information about insurance

a. Whether the trial is covered by the patient compensation scheme or if a separate insurance policy is taken out.

The trial is covered by the patient compensation scheme (Patienterstatningen).

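### Hyperexcitability is defined by IED presence with no time window, so IEDs after epilepsy onset can count as predictors and longer-recorded survivors are likelier to be positive

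*Protocol*

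**What the plan says.** The title in section 1 presents the exposure as a predictor: "Hyperexcitability as a Predictor of Epilepsy Risk in Glioblastoma". Section 2a lists development of epilepsy, seizure control, overall survival (OS) and progression-free survival (PFS) as endpoints.

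Section 3a gives the exposure rule: "Neuronal hyperexcitability will be defined as the presence of IEDs on the scEEG". The protocol text gives no window, IED count or rate, minimum recording time, or order relative to the first seizure, ASM start or progression. The timing it does give is:

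- Implantation (section 3a): "The scEEG will be inserted in the period from end of radiotherapy till first MRI evaluation after two cycles of adjuvant chemotherapy".
- Start of recording (section 3a): "Recordings from the device will start after implantation".
- End of recording (section 3b): "The scEEG will be explanted after fifteen months with the possibility of extension in case the scEEG device is approved for longer implantation".
- Wear (inclusion criteria, section 5a): "day and night for the duration of the study".

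Section 5b excludes patients with diagnosed epilepsy or on ASM. Epilepsy onset therefore falls after enrolment, and nothing stops the recording when it occurs. Section 8b collects seizures, ASM start and end dates, and the dates of progression and death from patient records.

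**The concern.** A predictor has to be measured before the outcome it predicts. A presence rule with no window, applied to a recording that continues past the outcome, allows two errors.

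- **Reversed order.** A patient whose first IED follows the first seizure or ASM start is classed as hyperexcitable and counts as a correct prediction. Section 2b itself notes that the EEG of a patient with epilepsy can show IEDs, so the outcome can produce its own predictor.
- **Guarantee time.** A patient can become IED-positive only while alive and recorded. Early death leaves less time to turn positive, so long survivors collect in the positive group even if IEDs have no bearing on survival. Differences in implantation date, wear time and any device extension add to the unequal recording time.

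The errors pull in opposite directions relative to the study hypothesis. The first favours the expected link with epilepsy. The second makes IED-positive patients look longer-lived, whereas section 2a expects a poorer prognosis.

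**Working it through.** **1. The protocol's own figure.** Section 4a gives 14 patients: one-sided 2.5%, power 80%, accuracy 0.5 under the null, sensitivity 85%. A one-sample normal approximation with p0 = 0.50 and p1 = 0.85 reproduces it: n = [(1.96 × √(0.5 × 0.5) + 0.842 × √(0.85 × 0.15)) / 0.35]² = 13.39, rounded up to 14. No exposure window enters this formula. The exact binomial test at n = 14 rejects at 12 or more correct (one-sided level 0.65%).

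**2. Simulation with no true association.** Assumptions, none from the protocol except the fifteen months:

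- Times from implantation to death, first IED and epilepsy are independent and exponential.
- Medians are 11-15 months for survival, 5-15 for first IED and 15 for epilepsy.
- Recording ends at death or 15 months, whichever is first. Positive means a first IED before that end; epilepsy means onset before that end.
- The OS hazard ratio is (deaths ÷ person-time in positives) ÷ (deaths ÷ person-time in negatives), with follow-up to death.

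| Quantity | True value | Result |
|---|---|---|
| Odds ratio, any IED v. epilepsy | 1 | about 1.6-2.5 |
| First IED after epilepsy, among patients with both | – | 40-50% |
| OS hazard ratio, positive v. negative | 1 | about 0.39-0.66 |
| Same two ratios with a 6-week landmark | 1 | about 1.0 |

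A separate set of assumptions (30-70% of patients positive by 15 months if still recorded, median survival 9-15 months, follow-up stopped at 15 months) gives a death-rate ratio of 0.34-0.45, again with a true value of 1. In that set, 6-20% of patients followed for under 6 months are positive, against 30-70% of those followed for the full 15 months. PFS was not simulated; the mechanism is the same but its size was not estimated.

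**3. Effect on the accuracy test.** This depends on the assumption made.

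- Under the independent times of step 2, accuracy is about 0.53-0.61, and the test at n = 14 rejects in about 1-5% of studies.
- Suppose instead that a share b of all patients shows IEDs regardless of later epilepsy, and a share q of epilepsy patients shows IEDs after onset. Then apparent sensitivity = 1 − (1 − b)(1 − q), and with 50% epilepsy, accuracy = 0.5 × sensitivity + 0.5 × (1 − b).
  - b = 0.1, q = 0.9: sensitivity 1 − 0.9 × 0.1 = 0.91; accuracy 0.455 + 0.45 = 0.905; rejection 86%.
  - b = 0.3, q = 0.7: sensitivity 1 − 0.7 × 0.3 = 0.79; accuracy 0.395 + 0.35 = 0.745; rejection 27%.
  - Using pre-onset IEDs only, accuracy is 0.5b + 0.5(1 − b) = 0.50 and rejection 0.65%.

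**4. Patients lost at a 6-week landmark (1.5 months), assumptions of step 2.** For the epilepsy question, the share with death or epilepsy before the landmark is 1 − exp[−0.693 × 1.5 × (1/median survival + 1/15)].

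- Survival median 15: 1 − exp(−0.139) = 13%.
- Survival median 11: 1 − exp(−0.164) = 15%.

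Of 14 patients that is 1.8 to 2.1, so about 2.

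**The case against.** The strongest reply is that the protocol defines only the signal that marks hyperexcitability. It does not say which recording epochs count for which endpoint, and it specifies no survival model. Landmarks and time-dependent covariates are commonly left to the SAP, which is not at hand. The data for a time-ordered analysis are already planned, and the study calls itself explorative.

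Much of this is fair, and it limits the point. It does not remove it: the protocol itself fixes its central exposure and attaches a formal accuracy hypothesis to hyperexcitability. An SAP that added a window would be narrowing the protocol's definition, not filling in a detail.

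A reader might infer more than the text supports:

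- **That the protocol commits to an ever/never classification and scores short recordings as negative.** Neither is written. The first is the plain reading of a presence rule without a window; the second is only a possible consequence.
- **That predictor and outcome come from the same recording.** Section 2b says of the device that "we will use it as an instrument to continuous, long-term, EEG monitoring to improve the detection of IEDs and seizure activity", but section 8b takes seizures from patient records. The protocol does not say that device-detected seizures define epilepsy.
- **That IEDs after onset should never count.** Seizure control has meaning only once epilepsy has begun, so later IEDs are legitimate for that endpoint.
- **That the 14-patient test is bound to give a false positive.** Depending on the assumption, false rejection runs from about 1% to 86%, and the protocol gives no rates with which to choose.

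**Conclusion.** The point holds as a defect in the exposure definition for the epilepsy-prediction, PFS and OS questions. Under its plain reading, the rule lets IEDs that follow epilepsy count as predicting it, and it favours patients who survive and record longer.

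The guarantee-time mechanism for OS does not depend on the assumed medians, since a patient must be alive and recorded to turn positive. The protocol's cited median survival of 15 months is about as long as the recording, so death will cut many recordings short. The sizes (odds ratio about 1.6-2.5, OS hazard ratio about 0.39-0.66) do rest on assumed medians and on independent exponential times. With 14 patients, an odds ratio of that size could hardly be told apart from 1. The reason to act is therefore that a result obtained under this rule could not be interpreted as prediction, rather than that a particular false finding is likely.

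**What to change.** For the epilepsy-prediction, PFS and OS questions, fix one of the following in writing before the recordings are read:

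1. **Early window with landmark.** Classify IED status from a fixed period of recording after implantation and count outcomes from its end. For the epilepsy question, leave out patients with epilepsy or ASM start before the landmark (and those who died before it). For PFS, leave out those with progression or death before it. For OS, leave out only those who died before it.
2. **Time-dependent covariate.** Let IED status change from negative to positive at the first IED, counting only IEDs before the event.

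Simply discarding IEDs after onset, while keeping one yes/no label per patient, is not enough: patients with epilepsy would then have the shorter time in which to turn positive.

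In either case, state which window the assumed 85% sensitivity refers to, and report IED rate per recorded hour to allow for unequal recording time. State that later IEDs are used for seizure control.

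The cost is mainly wording, since the recordings and dates are already collected. The landmark loses a few early events (about 2 of 14 patients at 6 weeks under the assumptions above), and a short window gives up some of the sensitivity to rare IEDs that motivates the device. The time-dependent version avoids both losses, but it yields no per-patient sensitivity, so the accuracy test in section 4a would still need a stated window.
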